2.3 Sample and Consent

Study participants were recruited from all middle school students (grades 6-8) in Blatchley Middle School in Sitka, Hoonah City School in Hoonah, and Dzantik'i Heeni Middle School in Juneau. The program enrolled 11 participants in Sitka, 20 in Hoonah, and 19 in Juneau for a total of 50 participants across communities. Research participation was not required to participate in the education program, and students opted into the survey and interview research components through a tiered informed consent process. Written consent was obtained from parents after information on research activities was shared, and verbal consent was obtained from participants before data collection activities. Of the 50 study participants, all consented to participate in the surveys and all but one consented to participate in the interviews. Participants in either or both research components were offered a \$10 cash card incentive for each lesson attended, with a total possible incentive of \$100 for attending all ten lessons. Incentives were used to encourage program participation and regular attendance.

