2.5 Survey Data Analysis

2.5.1. Accounting for Missing Data

Missing data at the person-visit level were imputed for age (n missing = 6) and each of the questions (n missing = 9-20, depending on question), treating each person-visit as a separate observation. The predictor variables in the imputed model included all question responses and all regression model predictors: age, gender identity, Alaska Native identity, and site. We used listwise deletion, excluding cases from analysis if data was missing, for gender (n missing = 10), Alaska Native identity (n missing = 6), and pre-post-program differences (n missing = 9-15, depending on question). No site data was missing. We generated 80 imputed

datasets via multiple imputation by chained equations (Azur et al., 2011). Across our models, the largest average relative increase in variance (RVI) due to nonresponse was 0.44 and the largest fraction of missing information (FMI) was 0.55, suggesting that our analysis based on 80 imputed datasets was reasonable. Statistical analyses were conducted using STATA 18.0 M/P (StataCorp, 2023).

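### As listed, the imputation model omits survey visit, the student's other-visit answer and lessons attended, so the mean pre-post change can be biased in either direction

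*Combined protocol and SAP*

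**What the plan says.** Section 2.5.1 describes two treatments of missing data.

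- **Imputation.** Chained equations fill in age and "each of the questions (n missing = 9-20, depending on question), treating each person-visit as a separate observation". On the model's content it says: "The predictor variables in the imputed model included all question responses and all regression model predictors: age, gender identity, Alaska Native identity, and site". The list names no pre/post indicator, no answer from the same student's other visit, and no measure of attendance.
- **Deletion.** The text reads "We used listwise deletion, excluding cases from analysis if data was missing, for gender (n missing = 10" and continues to Alaska Native identity and "pre-post-program differences (n missing = 9-15, depending on question".

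The only diagnostics are a largest average relative increase in variance of 0.44 and a largest fraction of missing information of 0.55, offered in support of 80 imputations. The documents give no reasons for missingness, no split by visit and no sensitivity analysis.

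On the denominator, section 2.3 says: "The program enrolled 11 participants in Sitka, 20 in Hoonah, and 19 in Juneau for a total of 50 participants across communities", and "Of the 50 study participants, all consented to participate in the surveys". It also offers a "cash card incentive for each lesson attended", over ten lessons.

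Section 2.2 makes the pre- and post-program surveys the primary outcome measure. Section 2.5.2 estimates the mean change by a linear GEE on clustered pre and post answers. Section 2.5.3 relates change in beliefs to change in intentions.

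**The concern.** The design has no comparison group, so the pre-post coefficient is itself read as the program's effect. An imputation model should contain the term whose coefficient is being estimated. If visit is absent, a missing post-program answer is drawn from a mixture of pre and post answers, and the change shrinks.

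Treating the two visits as unrelated rows also discards what is usually the best single predictor of a missing answer: the same student's answer to the same item at the other visit.

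Attendance matters for a different reason. It measures how much of the program a student received, and it is a plausible cause of absence from an end-of-program survey. If low attenders were missing more often and also changed less, imputing them like other students overstates the change.

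The two effects work in opposite directions, and nothing in the plan shows the size of either. The deleted differences raise the same question for section 2.5.3, where imputation does not help because the incomplete pairs are dropped.

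**Working it through.** **1. The plan's own figures.** Enrolment is 11 + 20 + 19 = 50, as stated. Missing differences are 9/50 = 18% to 15/50 = 30%. Missing imputed answers are 9/100 to 20/100 = 9-20% of person-visits, if the base is 50 students x 2 visits (an assumption; the base is not stated). A common rule asks for at least 100 x 0.55 = 55 imputations, and the relative efficiency of 80 is 1/(1 + 0.55/80) = 0.993. So 80 is enough to control simulation error, but that says nothing about what the imputation model should contain.

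**2. Share missing at the post visit (p).** This is not reported. A student with no post answer to an item has no difference for it. If both counts refer to the same 50 students, p is therefore at most 15/50 = 30% for any item with a difference, and could be much lower if the gaps are at the pre visit. I use 18% and 30% as illustrations.

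**3. Visit left out.** Assume all pre answers are observed, a share p of post answers is missing unrelated to change, and the other predictors carry no information on visit. With true change D, the observed rows average D(1 - p)/(2 - p) above the pre mean, and missing post answers are imputed there.

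Estimated change = (1 - p)D + pD(1 - p)/(2 - p) = D x 2(1 - p)/(2 - p).

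- p = 0.18: factor 1.64/1.82 = 0.901, so D = 0.50 becomes 0.45.
- p = 0.30: factor 1.40/1.70 = 0.824, so D = 0.50 becomes 0.41.

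**4. Visit included, attendance left out.** Overstatement = p x d, where d is how far the mean change in the missing students falls below what was imputed. The d values are assumed.

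| p | d = 0.25 | d = 0.5 | d = 1.0 |
|---|---|---|---|
| 18% | 0.045 | 0.09 | 0.18 |
| 30% | 0.075 | 0.15 | 0.30 |

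**5. Both together.** I ran a large-sample simulation (200,000 students) of one item. All settings are assumptions: true mean change 0.50, SD 1, within-person correlation 0.5, attendance binomial with 10 lessons at probability 0.75, and log-odds of a missing post answer falling 0.6 per lesson. Imputation was by regression mean. Entries are the estimated change at 18% / 30% missing; the realised true change was 0.498-0.503.

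| Change per extra lesson (points) | Neither visit nor attendance | Visit only | Pre and post linked, with attendance |
|---|---|---|---|
| 0 | 0.453 / 0.412 | 0.503 / 0.501 | 0.503 / 0.502 |
| 0.1 | 0.467 / 0.439 | 0.518 / 0.532 | 0.498 / 0.501 |
| 0.2 | 0.487 / 0.465 | 0.541 / 0.564 | 0.502 / 0.502 |
| 0.3 | 0.503 / 0.491 | 0.559 / 0.596 | 0.500 / 0.503 |

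With visit omitted, the change is understated or, at the strongest attendance effect, roughly right because the two errors offset. With visit included, leaving out attendance does no harm if change does not depend on it, and overstates by up to about 0.06 / 0.09 at 0.3 points per lesson.

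**The case against.** **The predictor list may be shorthand.** Visit is the key term of the section 2.5.2 model, and the analysts may have imputed with it without naming it. This stands as a possibility, and the downward bias would then disappear. It does not settle the matter: the list is introduced as complete, visit is not in it, and imputing each person-visit separately still excludes the student's own other-visit answer.

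**Attendance may not be in the research data.** Section 2.3 says only that payment was offered per lesson. Three organizations ran the program, and no section says counts were kept or linked to survey records. This stands: that attendance was counted is a strong inference, not a stated fact.

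**The mechanism is assumed.** No section says who was missing or why. Missing counts differ by question, so some gaps are probably skipped items in a returned survey, where the other answers at that visit do help. At 0.1 points per lesson, the illustrated upward bias is only 0.02-0.03 points. This stands and limits how strongly the point can be put.

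**A delta-adjusted analysis is an extra.** No shift value is anchored in the documents, and its absence is not an error. I agree, and the point does not rest on it.

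**Conclusion.** The point holds for the imputation model as described: it lacks visit, the student's other-visit answer and attendance, and the mean change in section 2.5.2 can be biased toward zero or upward as a result. The documents give no change estimates, standard deviations, attendance data or missingness by visit, so neither the size nor the net direction can be computed. The figures above rest on assumed values and show only that errors of several hundredths to a few tenths of a Likert point are possible.

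A reader might infer more: that 18-30% of the primary outcome was imputed without attendance, and that the program's effect is therefore overstated. The documents do not support either step. The 18-30% are pre-post differences that were deleted, not imputed, and they most naturally enter the section 2.5.3 models. An upward direction needs low attenders to be both missing more often and changing less, and it can be offset or outweighed if visit was also left out.

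**What to change.** 1. State whether visit and the student's other-visit answers entered the imputation. If not, re-run it with pre and post linked in one row per student, so that each answer is imputed from that student's own answer to the same item at the other visit.
2. Restrict the predictors for each item. Section 2.4 has 16 questions, two of them relevant only after the program, which gives 14 x 2 + 2 = 30 item columns for 50 students. Using all of them would not be stable.
3. Add lessons attended as an auxiliary variable if payment records can be linked to survey records.
4. For section 2.5.3, derive the differences from the imputed pre and post values instead of deleting incomplete pairs.
5. Report missingness by visit.
6. Optionally, repeat the section 2.5.2 GEE with imputed post answers lowered by 0.25, 0.5 and 1.0 points (assumed values), and report which items keep their conclusion.

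The cost is a re-run, the work of linking payment records, and fewer predictors per item than the present model uses. Some items may prove fragile. No new data collection is needed if the attendance counts exist.

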2.5.2. Pre-Post-Program Changes in Theory of Planned Behavior Beliefs and Behavioral Intentions

To evaluate pre-post-program changes in beliefs and behavioral intentions related to shellfish harvesting, consumption, and risk reduction, we tested the association between pre- and post-program responses (i.e., the intervention effect). We included covariates for site (Sitka, Hoonah, and Juneau), age, Alaska Native identity (Alaska Native, non-Native), and gender identity (girls, boys, and nonbinary). To consider within person pre-post-program changes in TPB Beliefs and behavioral intentions, we used generalized estimating equation linear regression (GEE) to cluster pre-post measures (Liang & Zeger, 1986). We also evaluated differences in pre-post-program changes in TPB beliefs and behavioral intentions among the three participating communities and Alaska Native and gender identities using interacted models. Results of interacted models are presented in appendix 3.

We present individual participants' responses to the one year post-program survey as the number of participants in this follow-up survey was small. When we closed the study on July 31, 2024, only 7 participants had completed the program at least one year prior and were available for one year post-program recontact, having completed the program in either fall 2022 or spring 2023 semesters. These participants were all from Sitka. Of these 7 participants, 4 completed the follow-up survey. One year post-program survey responses are presented in appendix 4.

2.5.3. Relationships Between Changes in Theory of Planned Behavior Beliefs and Changes in Behavioral Intentions

To characterize TPB constructs most influential in shifting planned behaviors, we again used GEE to test the association between pre-post-program changes in TPB beliefs and pre-post-program changes in harvesting and exposure risk reduction behavioral intentions. Similar to the models we used to assess pre-post-program changes, we adjusted for site, age, Alaska Native identity, and gender identity. We also adjusted for changes in other TPB beliefs related to either shellfish harvesting or exposure risk reduction, depending on the behavioral intention outcome.

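### The primary pre-post model deletes records with unreported gender or Alaska Native identity, losing any answers they hold for little or no gain; a 'not reported' category would keep them

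*Combined protocol and SAP*

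**What the plan says.** Section 2.2 makes the pre- and post-program surveys the primary outcome. Section 2.3 reports 50 students (11 Sitka, 20 Hoonah, 19 Juneau), all of whom consented to the surveys.

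Section 2.5.1 handles missing data in two ways:

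- **Imputed:** On age it says: "Missing data at the person-visit level were imputed for age (n missing = 6". Survey answers are handled the same way, with gaps reported for "each of the questions (n missing = 9-20, depending on question". The imputation ran with no link between a student's two visits: "treating each person-visit as a separate observation". Besides the answers themselves, the imputation predictors are "all regression model predictors: age, gender identity, Alaska Native identity, and site". Visit is not listed.
- **Deleted:** On gender it says: "We used listwise deletion, excluding cases from analysis if data was missing, for gender (n missing = 10". The same rule is applied to a second trait: "Alaska Native identity (n missing = 6".

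Section 2.5.2 gives the primary model: "we used generalized estimating equation linear regression (GEE) to cluster pre-post measures". On adjustment it says: "We included covariates for site (Sitka, Hoonah, and Juneau), age, Alaska Native identity (Alaska Native, non-Native), and gender identity". Interactions with site, identity and gender are fitted in separate models, reported in appendix 3.

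The methods text does not say whether the 10 and the 6 are students or person-visits, how far they overlap, or whether a trait reported at one visit was used at the other. The deletion for missing pre-post differences (9 to 15) appears to belong to the change-on-change models of section 2.5.3 and is not part of this point.

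**The concern.** Each student is their own control in the pre-post comparison. Adjusting for something that does not change within a student adds little to that comparison, yet here it is the reason records leave the analysis. Age is missing as often as Alaska Native identity (6 each) but is imputed, and the text gives no reason for the different treatment.

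At stake is the precision of the primary estimate in a sample of at most 50. The estimate is also limited to respondents who reported both traits, although every student consented to the surveys.

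**Working it through.** **1. Inputs.** From the document: 50 students, two visits, sites 11/20/19, gender missing 10, Alaska Native identity missing 6, answers missing 9 to 20 per question. Assumed, because not stated: outcome SD 1, true change 0.40, within-student correlation r from 0.3 to 0.7. The plan states no analysed N or power, so there is no figure to reproduce first.

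**2. Both visits present, covariates constant within student.** The visit term is then orthogonal to every student-level covariate. In a linear GEE with independence or exchangeable working correlation, the visit coefficient is the mean of the within-student differences, and its robust SE depends only on their spread. In one simulated dataset the coefficient was 0.45337 and the robust SE 0.14229 with visit, site and age. Both were identical with gender and identity added (either working correlation) and with 'not reported' categories (exchangeable). The text does not state the SE type; the model-based exchangeable SEs were 0.1414 and 0.1418.

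**3. When those conditions fail** (200 simulations each, true change 0.4).

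- With 10 of 50 post visits missing, removing the two traits moved the estimate by 0.011 on average in absolute terms (maximum 0.061).
- With age differing between a student's visits, the average was 0.016 (maximum 0.076).
- Deleting 10 students moved the estimate with an SD of 0.068 and raised the SE by a factor of 1.11.

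**4. Upper limits on the SE increase.** The deleted total is 10 if the 6 lie within the 10, and 10 + 6 = 16 if they do not overlap.

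| Meaning of the counts | Formula | Smaller total | Larger total |
|---|---|---|---|
| Students, both surveys answered (k = 10, 16) | √(50/(50−k)) | √(50/40) = 1.118 | √(50/34) = 1.213 |
| Person-visits in pairs (k = 10/2 = 5, 16/2 = 8) | √(50/(50−k)) | √(50/45) = 1.054 | √(50/42) = 1.091 |
| Single person-visits of m different students, split evenly (m = 10, 16) | √(50/[(50−m) + (m/2)(1−r)]) | 1.072 to 1.098 | 1.124 to 1.172 |
| Students who answered one survey only (k = 10, 16) | see below | 1.015 to 1.043 | 1.025 to 1.079 |
| Records with no answers | none | 1.00 | 1.00 |

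Third row, at r = 0.3 and m = 10: √(50/(40 + 3.5)) = 1.072. This loss becomes zero once the trait is carried over from the other visit.

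Fourth row: if the single surveys are split evenly, the factor is √([(50−k) + (k/2)(1−r)]/(50−k)). At k = 10 and r = 0.3 this is √(43.5/40) = 1.043. If all are the same survey, the variance before deletion is (1−r²)/(50−k) + (1−r)²/50 and after deletion 2(1−r)/(50−k). At k = 10 and r = 0.7 the factor is √(0.015/0.01455) = 1.015.

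**5. Could all deleted records be blank?** If both trait counts use the same unit, at least 10 − 6 = 4 gender-missing cases reported identity, so they are not wholly blank. The least-missing question is missing 9 times. If that count and the gender count refer to the same records, at least 10 − 9 = 1 deleted record holds an answer to it. Beyond that, the text does not show how many answers are lost.

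**6. Dropping the traits or keeping them with 'not reported'.** Suppose 24% of post visits are missing, 40% in one gender and 8% in the other, with a gender effect of 0.5 SD (600 simulations, exchangeable, true change 0.40). Without gender the estimate averaged 0.36 at r = 0.3 and 0.5. With gender it averaged 0.395 and 0.386. In separate simulations with 10 students missing gender (60 runs per setting), carrying traits over and using 'not reported' kept every observed answer. It stayed centred near the true change under such dropout and had lower root mean squared error than deletion.

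**7. Why the missing-answer rule matters.** With 10 trait-missing students lacking a post visit, person-visit imputation without visit as a predictor shrank a true change of 0.40 to 0.352, 0.356 and 0.361 at r = 0.3, 0.5 and 0.7 (3,000 simulations). Observed answers only, or imputation with one record per student, gave an SD slightly below that of deletion (0.181 and 0.182 against 0.187 at r = 0.3).

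**The case against.** Four arguments have weight.

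- **The exact result needs conditions the trial may not meet.** Answers are missing, and age is imputed by person-visit, so it can differ within a student. This stands: 'no change' becomes 'generally a slight change'.
- **The traits can protect the estimate when missing visits depend on a trait.** This stands (step 6). A reader might infer that gender and identity are useless and should simply be dropped. The documents do not support that, because they do not say whether missing visits are related to either trait.
- **No loss is demonstrated.** This stands as to size. A reader might infer that 10 to 16 students were lost and that the primary analysis rests on 34 to 40. The text supports that only if the counts are students, and the 12% to 21% figure also needs all of them to have answered both surveys. Analysed Ns may be in results or appendices not supplied here, so their absence from the methods text is not a fault in itself.
- **A common adjusted sample across the primary, interacted and section 2.5.3 models is a reasonable choice.** This is fair, and the interacted models do need reported identities. It does not require the primary estimate to be confined to that sample when a 'not reported' category avoids it.

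**Conclusion.** The point holds as a cheap improvement. The primary pre-post GEE deletes records for want of two fixed traits whose main effects do little or nothing for the pre-post coefficient, so any answers in those records are lost for little or no gain.

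The size is unknown. The SE is at most 12% to 21% wider if the counts are students with both surveys answered, about 5% to 9% if they are paired person-visits, and near zero if the deleted records are almost blank. The other readings in the table fall within this range. The figures assume a common outcome variance and, where r appears, a correlation of 0.3 to 0.7.

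A reader might infer that the deletion biases the result. Nothing in the documents shows that students with unreported traits changed differently from the rest, so no bias is claimed. The interacted models are outside this point.

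**What to change.** 1. Where a trait or age is reported at one visit, carry it to the same student's other visit.
2. Keep gender and Alaska Native identity in the primary GEE with a 'not reported' category, and stop deleting records for them, so that every observed answer is used. Dropping the two traits should not be the first choice.
3. Apply one missing-answer rule to all students in that model: either observed answers only, or a re-imputation with pre and post answers on one record per student. Do not mix rules.
4. Show the current listwise-deleted model alongside. Label the new model as post hoc, since the study closed on July 31, 2024 (section 2.5.2). Leave the interacted models on reported identities.
5. State the unit and overlap of the 10 and the 6, and the analysed N per model if the results do not already give it.

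Cost: no new data and one re-run per question. If imputed answers are used, a re-imputation is also needed, because age and both traits are predictors in the existing one. The primary sample would differ from that of the interacted and section 2.5.3 models, which should be stated in the report.

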2.5.2. Pre-Post-Program Changes in Theory of Planned Behavior Beliefs and Behavioral Intentions

To evaluate pre-post-program changes in beliefs and behavioral intentions related to shellfish harvesting, consumption, and risk reduction, we tested the association between pre- and post-program responses (i.e., the intervention effect). We included covariates for site (Sitka, Hoonah, and Juneau), age, Alaska Native identity (Alaska Native, non-Native), and gender identity (girls, boys, and nonbinary). To consider within person pre-post-program changes in TPB Beliefs and behavioral intentions, we used generalized estimating equation linear regression (GEE) to cluster pre-post measures (Liang & Zeger, 1986). We also evaluated differences in pre-post-program changes in TPB beliefs and behavioral intentions among the three participating communities and Alaska Native and gender identities using interacted models. Results of interacted models are presented in appendix 3.

We present individual participants' responses to the one year post-program survey as the number of participants in this follow-up survey was small. When we closed the study on July 31, 2024, only 7 participants had completed the program at least one year prior and were available for one year post-program recontact, having completed the program in either fall 2022 or spring 2023 semesters. These participants were all from Sitka. Of these 7 participants, 4 completed the follow-up survey. One year post-program survey responses are presented in appendix 4.

2.5.3. Relationships Between Changes in Theory of Planned Behavior Beliefs and Changes in Behavioral Intentions

To characterize TPB constructs most influential in shifting planned behaviors, we again used GEE to test the association between pre-post-program changes in TPB beliefs and pre-post-program changes in harvesting and exposure risk reduction behavioral intentions. Similar to the models we used to assess pre-post-program changes, we adjusted for site, age, Alaska Native identity, and gender identity. We also adjusted for changes in other TPB beliefs related to either shellfish harvesting or exposure risk reduction, depending on the behavioral intention outcome.

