2.4 Survey Design

A five-point (1-5) Likert scale survey was administered to participants at the beginning and end of the program, as well as one year after program completion. The instrument used in

these three instances of data collection included 16 questions relevant to the three types of TPB beliefs—behavioral beliefs (attitudes toward the behavior), normative beliefs (perceived attitudes of peers and respected figures toward the behavior), and control beliefs (perceived ability to perform the behavior)—and was divided into two sections. In the first section, on shellfish harvesting, questions asked about participants' perceptions of and experience with shellfish harvesting, perceptions of peers' views about shellfish harvesting, and sense of agency and behavioral intentions related to engaging in shellfish harvesting. For example, related to normative beliefs: "Most of the people who are important to me would approve of me participating in subsistence clam harvesting" (disagree – agree Likert scale). In the second section, on checking toxin levels using the SEATOR website, questions asked about participants' perceptions of this risk reduction behavior, perceptions of peers' views about checking toxin levels, and sense of agency and behavioral intentions related to checking toxin levels. For example, related to control beliefs: "I am confident that I can check the SEATOR website before clam harvesting" (disagree – agree Likert scale). In both sections, the last question asked about behavioral changes related to program learning and thus was relevant in only the post-program survey. Full survey response data is presented in appendix 2.

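### The interacted GEE models in section 2.5.2 compare pre-post change across small groups with no stated small-sample correction, so false subgroup differences are more likely than the nominal 5%

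*Combined protocol and SAP*

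**What the plan says.** The main pre-post analysis is a linear GEE: "we used generalized estimating equation linear regression (GEE) to cluster pre-post measures (Liang & Zeger, 1986". Section 2.5.2 then asks whether change differs "among the three participating communities and Alaska Native and gender identities using interacted models", and sends those results to appendix 3. The gender factor has three levels: "gender identity (girls, boys, and nonbinary".

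Section 2.3 gives the site sizes: "The program enrolled 11 participants in Sitka, 20 in Hoonah, and 19 in Juneau for a total of 50 participants across communities". Section 2.5.1 says that cases were excluded where data were missing "for gender (n missing = 10), Alaska Native identity (n missing = 6", and also for missing pre-post differences (9 to 15, depending on the question). Missing question responses and age were imputed.

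Sections 2.5.1 and 2.5.2 do not state the variance estimator (robust or model-based), the working correlation, the reference distribution, a small-sample correction, a minimum cell size, the number analysed in each subgroup, or any multiplicity handling or exploratory label for the interaction tests. Section 2.5.2 does treat small numbers as a reason to show individual responses instead of a model, but only for the one-year follow-up.

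**The concern.** GEE inference with z critical values is a large-sample method in the number of clusters, and here the clusters are students. In an interacted model, the estimated change in a subgroup rests on that subgroup's own students. The robust variance is then biased downward and noisy, and a normal reference ignores the noise. The smaller the cell, the worse both effects become.

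Appendix 3 is where the plan answers whether a community or an identity group responded differently. If its standard errors are too small, a named community or a small gender group may be reported as different when it is not. Calling the results exploratory would not correct the standard errors.

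**Working it through.** The document gives no alpha, power or effect size for these tests, so there is no stated figure to reproduce. I take two-sided 5%.

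**Inputs from the document.** Sites of 11, 20 and 19 students (section 2.3); three gender levels (section 2.5.2); 16 survey items (section 2.4), of which the last in each of two sections applies only after the program, leaving 16 − 2 = 14 with a pre-post change.

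**Assumed.** Nonbinary counts of 2 to 8; sites of 8/16/15 as an illustration of losses; equal spread unless stated otherwise.

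**Step 1: the contrast.** With two complete visits, the visit-by-group coefficient is the difference in mean within-student change between two groups of sizes a and b. Its true variance is σ²(1/a + 1/b). The robust variance with the usual N/(N − 1) factor has expectation

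σ² × [((a − 1)/a)/a + ((b − 1)/b)/b] × N/(N − 1).

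- Sitka against Hoonah (11, 20; N = 50): true 1/11 + 1/20 = 0.1409. Expected robust (0.0826 + 0.0475) × 50/49 = 0.1328. Ratio 0.94.
- A cell of 5 against an assumed 18: true 0.2556. Expected robust (0.1600 + 0.0525) × 50/49 = 0.2168. Ratio 0.85.
- A cell of 2 against 18: true 0.5556. Expected robust (0.2500 + 0.0525) × 50/49 = 0.3086. Ratio 0.56.

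**Step 2: false-positive rates by simulation, no true difference.** The complete-data figures come from runs with 1-5 Likert or normal responses. The adjusted figures come from a full linear GEE with exchangeable correlation, covariates and 10% of visits missing at random. Monte Carlo error is about 0.3 points or less for complete data and 0.5 to 1.1 points for the adjusted model.

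| Difference in change | Robust SE, z | Model-based SE, z |
|---|---|---|
| Sitka, 11/20/19, complete | 7% | 6% |
| Sitka, assumed 8/16/15, complete | 8% | 7% |
| Sitka, adjusted GEE | 8-9% | 7-9% |
| Nonbinary, assumed n = 5, complete | 11% | 7% |
| Nonbinary, n = 4, complete | 13-14% | 6% |
| Nonbinary, n = 3, complete | 18% | 7% |
| Nonbinary, n = 2, complete | 28-29% | 6% |
| Nonbinary, adjusted GEE, n = 8, 5, 3 | 10%, 14%, 23% | 7-8% |
| Alaska Native identity, adjusted GEE | 6-7% | 6-7% |

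The joint robust test for site gives 7.9% (11/20/19) and 9.6% (8/16/15).

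**Step 3: candidate remedies.**
- A Mancl-DeRouen corrected SE with z, in the adjusted GEE, gives about 5 to 7% for Sitka and 7% for a nonbinary cell of 5 or 8, but still about 12% at 3.
- A pooled-variance t or F test on change scores gives about 5% at equal spread. If the small group's change has 1.5 times the SD of the others, it gives about 10% for Sitka (robust z: 7.4 to 7.9%) and 14% for a cell of 5 (robust z: 13%). At 2 times the SD it gives 14% and 22%, against 8% and 14%.
- An unequal-variance SE with t or F degrees of freedom to match gives about 5% for Sitka at every spread tried.

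**Step 4: multiplicity.** Taking one joint test per item and factor, 14 × 3 = 42 tests. At a true 5%, 42 × 0.05 = 2.1 false positives are expected. If the tests were independent, which they are not, the chance of at least one would be 1 − 0.95^42 = 88%.

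**The case against.** The strongest case on the other side is that the only documented small cell, Sitka, shows mild inflation, and that the large figures need two undocumented facts together: a robust SE and about five or fewer nonbinary students. That stands. The losses "for gender (n missing = 10" are not broken down by site, and it is unclear whether they count students or person-visits, so no analysed Sitka size below 11 can be derived. Appendix 3 cannot be seen here and may give counts, SE type or caveats. These are additional analyses, the main pre-post estimate is untouched, and multiplicity is at least as large a source of false positives.

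A reader might go further and use P(|t with n − 1 df| > 1.96 × √((n − 1)/n)), which gives 9.1% at n = 11, 15.4% at n = 5 and 39.8% at n = 2. That formula tests one subgroup's own change against zero. The plan tests differences in change, where the comparison group's variance also enters, and the rates are lower (step 2). For the same reason, a single-student cell does not bring the SE of the tested difference to zero.

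What the objection does not remove is that the rate for Sitka exceeds 5% under either SE type, and that the text does not let a reader tell which rate applies to gender.

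**Conclusion.** The concern holds in moderate form. With z inference and equal spread, the Sitka difference in change has a false-positive rate of about 6 to 9% instead of 5%, whichever SE was used. The nonbinary difference ranges from about 6 to 8% (model-based SE) to 11%, 13%, 18% or 28% with complete data (robust SE and an assumed 5, 4, 3 or 2 students). Uncorrected multiplicity adds to this.

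A reader might infer that spurious subgroup differences did appear, or that the nonbinary cell is known to be very small. The document supports neither: it gives no interaction result and no nonbinary count. False differences are more likely, not demonstrated. The figures also leave out the multiple-imputation step, which could move them either way.

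**What to change.** Rerun the appendix 3 interaction tests with a small-sample corrected variance that allows unequal spread, and with Satterthwaite-type t or F degrees of freedom. For two visits, a regression of within-student change on the factor with such an SE targets the same contrast. Keep the imputed responses and the covariates, since deleting incomplete pairs would shrink the cells further. Do not rely on pooled variance alone, because it rejects too often if the small group is more variable.

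Report one joint test per factor, and state the number of tests and that they are exploratory. Give analysed cell counts and the SE type. For very small cells (under 5 students, for example; the cutoff is a judgement) show n and mean change without a p-value. This follows the plan's own handling of the small one-year follow-up.

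The cost is a rerun of the appendix 3 models and a few sentences in section 2.5.2, with no new data. The downside is wider intervals and no formal test for the smallest cells.
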